Study Protocol and Statistical Analysis Plan

Evaluation of Retinal Microvascular Change That May Develop in After Open Globe Injury

NCT05771467

November 27, 2023

Objective: To evaluate the effect of open globe injury on anterior chamber, intraocular pressure measurements, retina and choroidal microvascular circulation in the unaffected eye; and to compare results among healthy age-matched individuals.

Methods: This prospective case-control study was approved by the local ethics committee of the Akdeniz University Faculty of Medicine (Approval Number: 2021-162) and the study was conducted in compliance with the ethical standards set out in the Declaration of Helsinki. Informed consent was obtained from the participants who agreed to participate in the study. All subjects underwent a comprehensive ophthalmologic examination, which included refractive error (Nidek ARK-700A, Nidek Co., Ltd, Gamagori, Japan), best corrected visual acuity (BCVA), IOP/Fully Automatic Tonometer, NIDEK NT-2000, Nidek Co., Ltd., Aichi, Japan), biometry and axial length (AL) (IOLMASTER 500, Carl Zeiss Meditec AG, Jena, Germany), slit-lamp examination of the anterior and posterior segments, Scheimflug Topography (Pentacam Oculus Optikgeräte GmbH, Wetzlar, Germany), and retinal and choroidal thickness and microvascular circulation of the retina and choroid were measured and recorded with Swept-Source Optical Coherence Tomography AngioTM (Topcon Corp, Japan). The BCVA was converted into the logarithm of minimal angle resolution (logMAR). Of the individuals included in the study, anterior chamber depth (ACD), anterior chamber volume (ACV), central corneal thickness (CCT), thinnest corneal thickness (TCT), astigmatism value (AST), corneal volume (CV), axial length (AL), spherical equivalent (SFEQ), intraocular lens power (ILP), VA (visual acuity), central retinal thickness (CRT), central choroidal thickness (CCT), superficial retinal circulation (SRC), deep retinal circulation (DRC) and choriocapillaris circulation (CC) data were recorded. The patients were followed for approximately six months, examined at one week, one month and three months after the trauma, and a total of three measurements were taken from the subjects. One measurement was taken from the control group.

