Statistical Analysis Plan (SAP): Statistical analyzes were performed using the IBM SPSS package, version 23.0 (SPSS Inc., Chicago, IL, USA). The Shapiro-Wilk test was used to analyze the normality of sample distribution. To define the sample, normally distributed values are presented as means \pm standard deviation, and non-normally distributed values are presented as median (minimum–maximum). The two-way repeated measures ANOVA test was used to examine the time-dependent change of the data. For the analysis of independent data, the independent-sample t-test and Mann-Whitney U test were used. For the analysis of

correlation, Spearman's correlation coefficient was used. The results were evaluated at a 95% CI. A level of $p < 0.05$ was accepted as statistically significant.

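### Controls are age-matched, but the between-group tests use neither the matching nor age, so the patient-control comparison may be conservative or less precise than it could be

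*Combined protocol and SAP*

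**What the plan says.** The Methods section calls the design case-control ("This prospective case-control study was approved by the local ethics committee"), and the Objective says that the unaffected eyes are studied in order "to compare results among healthy age-matched individuals". Neither says how matching was done: individually or at group level, at what ratio, or within what age limits.

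The Statistical Analysis Plan (SAP) section names these inferential methods:

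- For separate groups: "For the analysis of independent data, the independent-sample t-test and Mann-Whitney U test were used". The sentence does not mention the patient-control contrast, but no other method is assigned to it.
- For time: "The two-way repeated measures ANOVA test was used to examine the time-dependent change of the data".
- Spearman's coefficient for correlation.

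Patients were seen three times ("a total of three measurements were taken from the subjects"). For controls, "One measurement was taken from the control group". A p-value under 0.05 "was accepted as statistically significant". No paired test, matched-set model or age covariate is mentioned.

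**The concern.** Matching on age makes the two groups alike in age, so age contributes less to chance variation in the difference between group means. An independent-sample test takes its error term from the full spread within each group, including the part due to age. The design may therefore buy precision that the analysis does not use.

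The main question is whether the unaffected eye differs from that of a healthy person. A test with too large a standard error, or with avoidable noise, leans towards finding no difference. The confidence interval around a null result would also be wider than necessary. The repeated measures ANOVA does not fill the gap: it is assigned to change over time, and controls have a single measurement.

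**Working it through.** **Inputs.** From the documents: age matching, the independent-sample tests and the 0.05 level (two-sided assumed). The plan states no sample size, power, SD or age-outcome correlation, so there is no figure of its own to reproduce. Assumed: 30 per group, a true difference of 0.65 SD, and age explaining a share R of a measure's variance, with R from 0 to 0.4.

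**Formula.** Let σ² be the variance of a measure within a group and n the number per group.

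- The t-test takes the variance of the mean difference as 2σ²/n.
- If patients and controls are matched exactly on age, the true variance is 2σ²(1−R)/n. The test's standard error is then too large by 1/√(1−R).
- If controls merely come from the same age distribution, the true variance is 2σ²/n and the t-test is correct. A model with age has a variance of about 2σ²(1−R)/n, so it is more precise.

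R is the square of the age-outcome correlation: a correlation of 0.3 gives R = 0.09 and 1/√0.91 = 1.048, while 0.5 gives R = 0.25 and 1/√0.75 = 1.155.

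**Close matching**, 30 per group, simulated. Type I error is given for exact age pairs, then for frequency matching within age quintiles. Power is for frequency matching; exact pairs give almost the same.

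| R | SE ratio | t-test type I error | Power, t-test | Power, group + age |
|---|---|---|---|---|
| 0.1 | 1/√0.9 = 1.05 | about 4%; 3.8% | 71% | 74% |
| 0.2 | 1/√0.8 = 1.12 | 2.9%; 3.1% | 72% | 79% |
| 0.3 | 1/√0.7 = 1.20 | about 2%; 2.2% | 73% | 84% |
| 0.4 | 1/√0.6 = 1.29 | 1.2%; 1.6% | 74% | 90% |

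The age-adjusted model keeps type I error at about 5% throughout. At R = 0.05, power is about 70% against 72%. At R = 0 there is no gain and no material loss.

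**Looser matching**, same assumptions. If controls only share the patients' age distribution, the t-test's type I error stays at 4.9% to 5.1%. If groups are called matched because mean age does not differ significantly, it runs from about 4.8% down to 3.8% as R goes from 0.05 to 0.4. Age adjustment still gains power: about 70% to 74% at R = 0.1. At R = 0.4, across all forms of matching, about 71% to 74% becomes about 90%.

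**Paired t-test**, 30 exact pairs, 0.6 SD difference. Against the independent t-test, its power is 61% versus 62% at a pair correlation of 0, 63% versus 63% at 0.05, 66% versus 64% at 0.1, 71% versus 64% at 0.2 and 77% versus 65% at 0.3. It gains nothing at low correlation because it has n−1 = 29 degrees of freedom instead of 2n−2 = 58.

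These simulations are for the t-test. The same reasoning applies to Mann-Whitney U, but its loss was not computed.

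**The case against.** The strongest reply is that being described as age-matched shows neither pairs nor equal ages. With loose matching the independent-sample test has the right variance, and adding age is an efficiency gain, not the correction of an error. This stands. A reader might infer that the design forces equal ages, so that the SAP's standard errors are wrong whatever was done. The documents do not support that, and the low type I error figures apply only to close matching.

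Second, the size is unknown. If the age-outcome correlation is at most 0.3, the standard error is at most about 5% too large even under exact matching, and the power at stake is small. None of the roughly 15 measures listed in Methods is shown to be strongly related to age. This also stands, so the range must start at zero. On the other side, the sponsor chose age as the matching factor, and nothing in the text suggests that age is irrelevant to every measure.

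Third, any error is in the safe direction: close matching does not bias the difference, and false positives are not inflated. True, but where the question is whether the fellow eye is affected, a missed difference is also a wrong answer.

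Uncertainty about the matching does not defeat the remedy. Age adjustment held its type I error and did not materially lose power under any form of matching tried.

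**Conclusion.** The point holds as a loss of precision of unknown size. The SAP's between-group tests use neither the matching nor age. For age-related measures they are conservative if matching was close, and valid but less precise than they could be if controls were drawn loosely from the same age distribution.

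Under the assumed 30 per group and 0.65 SD difference, age adjustment is worth about 0 to 2 power points for R up to 0.05, 3 to 4 at 0.1 and 15 to 20 at 0.4. The gain will differ from measure to measure.

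It would be too strong to say that real fellow-eye differences are missed. That needs a sample size, an age-outcome correlation and a true effect, and the documents give none of these. They support only that a difference may be missed.

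**What to change.** - State how controls were matched: individually or at group level, the ratio and the age limits.
- For patient versus control, replace the independent-sample tests with a linear model of each measure on group plus age, and report the age-adjusted difference with its 95% CI.
- Log-transform skewed measures where suitable. Otherwise use a rank-based age-adjusted test for the p-value only, because it does not give a difference in the measure's own units.
- If controls were individually matched, a paired or matched-set analysis is an alternative.

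**Cost.** A sentence or two in the SAP. Age should already be on record, since controls were selected on it. The covariate uses one degree of freedom and assumes that age acts linearly, which should be checked. The paired t-test costs more: n−1 degrees of freedom instead of 2n−2.
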